Secondary Analyses: We will compare the physical activity levels of participants in the two groups as measured by the hand grip dynamometer. We will also test the quality of life variables with the HADS and FACT-G tests. As each of these variables is also continuous and measured at the same points in time, we will determine the relationship of each of these variables to fatigue and analyze the data using repeated measures analyses as described above, testing for differences between groups, over time, and a time by group interaction. If several variables appear to be significantly related to fatigue, we will also perform multivariate analyses to determine the best predictors of fatigue as measured by the FACIT-F subscale. We will also determine relationships between daily or weekly fatigue, symptom data, and daily measures of sleep duration and fragmentation by determining correlation coefficients within time periods. Exploratory analyses of all subscale scores will be performed after the primary endpoint has been analyzed.

Summary information on the global symptom evaluation by group will also be provided at each of the assessed time points. Differences in distributions between groups will be analyzed using a chi-square analysis.

On an exploratory basis, we will also investigate whether or not different results were found for patients with different types of cancer, primarily using descriptive statistics. We do not expect to find statistical significance due to the low numbers of patients in each cancer type, but if we do find trends that appear to be significant, we will use this information to inform a future study. Additionally as a part of exploratory analysis, we will use Pearson chi-squared tests to compare the proportion of patients experiencing clinical benefit between each arm.

Information about toxic effects and tolerability will be summarized at each dose level. Safety assessments including hematology and chemistry assessments and toxicity evaluations will be made throughout the study (see Table 3).

For future investigational studies, analyses of the relationships between inflammatory cytokines and fatigue will also be performed using correlation analyses. The cytokines (serum and Induced monocyte) we will explore in future analyses include IL-1 β , IL-6, IL-10 and TNF- α . Information on cytokines and fatigue will be available at baseline, day 15 and day 29. We plan to explore the correlations between cytokines and fatigue within each time point and between time points.

D.10. Future Studies: The exploratory data gathered will be used to design a larger trial that will also allow for longer longitudinal follow-up of patients to determine the onset and duration of response;

determine whether response to ginseng occurs more frequently in patients with certain primary tumors or disease stages; and to determine adherence to assessments using different tools and timing of different evaluations. A larger study will also allow us to better characterize the role of cytokines versus direct central effects. The preliminary data obtained will allow us to design appropriate larger trials from the important information obtained regarding response, adherence to assessments using different tools, and timing of different evaluations. The trends observed for the secondary objectives of this preliminary study will allow us to conduct larger clinical trials and apply for future grant applications. The associations between symptom interventions as assessed using validated symptom assessment tools, objective measures such as Hand grip strength test and actigraphy, and levels of cytokines including monocyte induction, will justify for future fatigue studies.

D.11. Protection of Human subjects: We will obtain authorization for use and disclosure of Protected Health Information (PHI) from patients. This will be included in the written informed consent. We will follow The Health Insurance Portability and Accountability Act (HIPAA) guidelines during the study based on the following 3 criteria: 1) All research staff have completed research training concerning confidentiality of protected health information. Patient's name, social security number and other patient identifiers will not be used for data collection. Only protocol accession numbers will be used in data collection. The principal investigator will keep the collected data in a locked file cabinet; 2) Data collected for this study will be retained for 2 years after publication of the research and then it will be destroyed by a mechanic shredder; 3) The data will be used for this study and may be disclosed for use on other studies that have IRB-approval to access to the data. The data will not be disclosed to any other parties without an IRB-approved protocol and appropriate IRB-approved consent/authorization or waiver.

E. REFERENCES

- 1. Paice J. Assessment of symptom clusters in people with cancer. Journal of the National Cancer Institute Monographs No. 32, 2004; 98-102
- 4. Cleeland CS. Pain and symptom burden: lessons from patients with cancer. Presentation at the American Pain Society Meeting. Baltimore, MD, March 14-17, 2002; American Pain Society, Glenview, IL.
- 5. National Comprehensive Cancer Network Practice Guidelines. Cancer-Related Fatigue Panel 2006 Guidelines. Rockledge, PA: National Comprehensive Cancer Network; March 2006.

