allergies/hypersensitivities exist to Panax species, their constituents, or to other members of the Araliaceae family. Cardiovascular: Arterial hypertension has been reported. However, one double-blind study failed to find any effect on blood pressure [110]. In 1979, an article was published in the Journal of the American Medical Association that claimed that people can become addicted to P. ginseng and experience blood pressure elevations, nervousness, sleeplessness, diarrhea, and hypersexuality, this condition was termed as ginseng abuse syndrome [111]. However, this report has since been thoroughly discredited and should no longer be taken seriously[112,113]. One case report and one double-blind trial suggest that P. ginseng can reduce the anticoagulant effects of Coumadin (warfarin) [114,115], but another trial did not find such an interaction [111]. The reason for this discrepancy is not clear. Psychiatric: Concomitant use of *P. ginseng* and the monoamine oxidase inhibitor phenelzine (Nardil) may result in manic-like symptoms [39,116]. Hepatotoxic effects: Ginseng may increase the toxicity of hepatotoxic agents. Ginseng has been well tolerated in prior studies(Barton etal 2009). However possible interactions with hepatoxic agents (Miller LG Herbal medicinals: selected clinical considerations focusing on known or potential drug-herb interactions. Arch Intern Med 1998 Nov 9;158(20):2200) such as coumadin with reported increase in bleeding time. Hence we would monitor the PT/INR weekly for patients on coumadin and liver function test every 2 weeks (Total bilirubin </=1.5 mg/dL, and AST (SGOT) and ALT (SGPT) </=2 x ULN or </= 5 x ULN)if hepatic metastases are present or if patients are on potentially hepatoxic agents such as acetaminophen or statins. Patients with a history of hepatitis A, B and C will be excluded. Endocrine: There has been a few case reports of breast tenderness, postmenopausal vaginal bleeding, and menstrual abnormalities associated with Panax ginseng use [109,116]. Such side effects suggest that it has estrogenic properties. However, a large double-blind trial of P. ginseng found no estrogen-like effects [83] and a carefully designed in vitro study no estrogenic activity [120,121]. Ginseng decreased fasting blood glucose in both diabetic and non-diabetic patients and therefore combination use may lead to additive effects. Pregnancy and teratogeneity: Chinese tradition suggests that P. ginseng should not be used by pregnant or nursing mothers, and one animal study showed that ginseng use by a pregnant mother could cause birth defects [119-121]. In the proposed study, we plan to exclude patients with a psychiatric diagnosis, uncontrolled hypertension or arrhythmia, and diabetes; pregnant or lactating women; and patients taking anticoagulants, MAOIs [39,109], and tricyclic drugs. We will carefully monitor patients for adverse events and interactions with various medications, as described in Table 3.

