- 2. Rate fatigue on a numerical scale during the previous 24 hours as \geq 4 on a 0 to 10 scale (0 = no fatigue and 10 = worst possible fatigue).
- 3. Describe fatigue as being present every day for most of the day for a minimum of 2 weeks.
- 4. Memorial delirum assessment scale </= 13.
- 5. Are 18 years or older.
- 6. Hemoglobin level of ≥8 g/dL within 2 weeks of enrollment. If the patient has not had blood drawn for a hemoglobin level in the previous two weeks, one will be performed to determine eligibility. Patients with a hemoglobin level <9g/dL will be evaluated for treatment of anemia.

- 7. Able to understand and sign the informed consent.
- 8. No concurrent use of chronic systemic steroids (defined as currently on more than 1 week of treatment).
- 9. Controlled pain and depression symptoms, if present (defined as no change in the Morphine equivalent dose of 30% or change in the dose of antidepressant medication in the past 2 weeks)
- 10. Patients should have a Zubrod </= 2.
- 11. All patients who are receiving chemotherapy and/or radiation therapy are eligible for study if they have completed at least one cycle of chemotherapy or targeted therapy, or > 1 week of radiation therapy, and if they have been approved to go on study by their primary oncologist. The PI/designated research staff of this study will obtain and document approval from the primary oncologist and principal investigator of the clinical trial in case the patient is on another clinical trial as referenced in the patient's study documents.
- 12. Negative pregnancy test for women of childbearing potential, as defined by intact uterus and ovaries, and a history of menses within the last 12 months. Pregnancy test to be performed no greater than 14 days prior to consent in study. In cases of women with elevated b-HCG, these candidates will be eligible to participate so long as the level of b-HCG is not consistent with

pregnancy. Women of childbearing potential need to be on or use contraception, or be abstinent during the study period. Their male partners must also use contraception (condom) or maintain abstinence.

Birth controls specifications: Women who are able to become pregnant must use birth control during the study and for 30 days after the last ginseng/placebo dose.

Acceptable forms of birth control include barrier methods (such as condom or diaphragm) with spermicide.

C.3.2.2. Exclusion Criteria

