Patients will be randomly assigned to one of the two treatment arms. The randomization schema will be based on parameters input into RANLST, a randomization program developed at UTMD Anderson and supported by an NCI grant.

C.6. Clinical Trial Design and Treatment Plan:

This study will have (1) Phase I: an initial non dose escalating phase to evaluate dose limiting toxicity. A total 30 evaluable patients will be enrolled in this phase. After study completion of the 30 evaluable patients (2) Phase II a second phase- RCT double blind phase will be started and (3) Both phases will have an open labeled phase. Patients in both Phase I or II may continue the ginseng in the open labeled extension phase if there are no grade 2 or more toxicity as per CTRC criteria as determined by the PI. A

total of 158 eligible patients will be enrolled in both phases of the trial (30 evaluable in phase I + 128 in phase II). (See Study Design Fig. 6).

Evaluable patients will be defined as any patient enrolled on the study that has taken at least one dose of treatment (i.e., either ginseng or placebo), making them available for toxicity and response.

C.6.1. Double-Blind Phase Dosing Patients will be randomized to one of two experimental groups receiving the treatments detailed below.

- The placebo group (**Arm 1**), will receive oral placebo twice daily for 29 days.
- The Panax ginseng group (Arm 2) will receive ginseng capsules 400 mg twice daily for 29 days.

Unblinding Procedure:

- 1. The Statistician and the investigational pharmacist will have access to the codes/assignments.
- 2. The codes will be revealed only If there is a safety issue and the treating physician needs to be aware of the treatment assignment.
- 3. The PI should be contacted regarding and give approval for un-blinding
- 4. The Investigator/research team must inform the IND Office when un-blinding occurs.

C.6.2. Open-Label extension Phase

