The intervention phase of Phase I and II parts of the study will be followed by an open-label extension phase that will begin after the assessment on Day 29. Assessments of fatigue, physical activity, and psychosocial functioning will be conducted at baseline, day 15 and day 29. On Day 29, the study will be completed and patients will be given the option of continuing on an open label basis, Panax ginseng 800 mg per day, will be provided they have tolerated the double-blind phase without moderate to severe toxicity as per NCI CTC AE V4 criteria. All patients will be taken off the study on day 57. Patients will be followed for upto 30 days after the last dose of Panax ginseng.

"Baseline" evaluations, PE, history should be completed within 2 weeks prior to registration or 1 week prior to start of study drug(Table 3). The Drug compliance will be monitored with a pill diary and with weekly calls/ or in person meeting the patient by RN along with Toxicity evaluation (See Table 3). Toxicity evaluation, symptom assessment and medication review will include assessment toxicity using NCI CTCAE V4 criteria on Days 8, 15, 21, 29, 36, 43, and 57 (Table 3) (all +/- 3 days). Adverse events (including event name, grade, start/stop date and attribution) will be entered into PDMS/CORe, which will serve as the source documentation for adverse events. The Principal Investigator or physician designee will verify the attribution assigned in PDMS/CORe by signing the PDMS/CORe adverse events printout at the end of protocol treatment. PDMS/CORe will be used as the electronic case report form for this protocol. The unused drug returned will be documented in the shadow chart and destroyed as per institutional policy.

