Any Other non- hematologic toxicity assessed as Panax ginseng study drug or identical placebo - related ≥ Grade 2 including insomnia, anxiety, restlessness, behavioral change, dizziness, vertigo, tachycardia, diahhrea, nausea/vomitting, headache, increased menstrual bleeding and breast tenderness	 Hold (interrupt) dose. Follow at least weekly. If the toxicity resolves to ≤ grade 1 restart dose at (400mg) level and continue the study medication with continued monitoring as prescribed in the protocol. If the patient has repeat ≥ Grade 2 non-hematological toxicity, they will be discontinued from the study medication and monitored.

III. Discontinuation of Study Treatment

Treatment will continue until Day 29±3 and Day 57±3 for participants eligible for the open label phase.

Treatment with study drug is to be discontinued when any of the following occurs:

- Adverse event(s) that, in the judgment of the Investigator, may cause severe or permanent harm or which rule out continuation of study drug.
- Major violation of the study protocol.
- Withdrawal of consent
- Lost to follow up
- Death
- Suspected pregnancy

Major violation will be determined by the PI. Major violation will include lack of consent, lack of safety laboratory tests. These will be reported to IRB and FDA in a timely fashion.

Figure 6. Study Design

Phase I(1st 30 patients)

Table 3. Study Assessments

ASSESSMENTS	Baseline	Day 8 (± 3)Ph#	Day 15 (± 3)	Day 21 (± 3)Ph#	Day 29 (± 3)	Day 36 (± 3) Ph#	Day 43 (± 3)Ph#	Day 57 (± 3)
Medical History	Х							
Physical Examination	X							
Zubrod Score	Х							
Medication Review	Х	Х	Х	Х	Х	Х	Х	Х
Symptom and QoL Assessment								
ESAS	Х	Х	Х	X	Х	Х	Х	Х
HADS	Х		Х		Х			Х
FACT-G &FACIT-F subscale	X		×		X			X
SDMT	х		х		х			х
GSE**					x			х
Physical Activity								
6 minute walk test	X		X		X			X
Hand grip Strength and Endurance test	X		X		X			X
Hematology/ Chemistry*	X		X		X			X
Pregnancy Test [@]	Х							
Optional Blood	x		x		x			
Draws Toxicity Evaluation	X	X	X	X	X	X	X	X

* CBC, Electrolytes, Total bilirubin, and AST (SGOT) and ALT (SGPT will be done at Baseline, CBC and Electrolytes will be done at Day 15+/-3days and Day 29+/- 3days. We would monitor the PT/INR weekly for patients on coumadin and liver function test every 2 weeks (Total bilirubin, and AST (SGOT) and ALT (SGPT) if hepatic metastases are present or if patients are on potentially hepatoxic agents such as acetaminophen or statins.

**GSE - Global symptom evaluation

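### The only scheduled pregnancy test is timed to consent, not to first dose, so a compliant negative result can be 14 days old or more when dosing starts

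*Combined protocol and SAP*

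**What the plan says.** - **The rule for the test.** Criterion 12 (C.3.2.1) requires a negative test in women of childbearing potential and sets the timing: "Pregnancy test to be performed no greater than 14 days prior to consent in study". The footnote to the pregnancy-test row of Table 3 repeats the same sentence.
- **How often.** Table 3 marks the test once, in the Baseline column.
- **General baseline window.** C.6.2 says of baseline work in general: "evaluations, PE, history should be completed within 2 weeks prior to registration or 1 week prior to start of study drug(Table 3". The pregnancy test is not named there.
- **Contraception.** "Women who are able to become pregnant must use birth control during the study and for 30 days after the last ginseng/placebo dose". Criterion 12 adds: "Their male partners must also use contraception (condom) or maintain abstinence".
- **Stopping.** The list of reasons to discontinue treatment includes "Suspected pregnancy".
- **Why pregnancy matters here.** B.7 states that pregnant women are to be excluded. It cites Chinese tradition and reports that "one animal study showed that ginseng use by a pregnant mother could cause birth defects". The exclusion list in C.3.2.2 names nursing women but not pregnant women, so in the reviewed text criterion 12 is the eligibility rule that carries the exclusion out.

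**The concern.** A pregnancy test at entry is meant to show that a woman is not pregnant when she first takes study drug. What matters is the age of the negative result at first dose. The plan limits its age at consent instead and leaves the step from consent to dosing unlimited. A site can follow the rule exactly and still start drug on a result that is two weeks old or older.

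What is at stake is a small safety margin, not a trial result. The plan's own evidence of harm is limited: B.7 treats the exclusion as a precaution and also describes ginseng as apparently nontoxic in animals.

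**Working it through.** There is no plan figure to reproduce. The check is interval arithmetic on the stated rules.

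**Inputs**
- Look-back limit: 14 days, counted from consent (criterion 12 and the Table 3 footnote).
- General window: 14 days before registration, or 7 days before study drug (C.6.2).
- g = days from consent to first dose; r = days from registration to first dose. The reviewed text limits neither, so the values of g below are assumptions.

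**Step 1. The test's own rule.**
Age at first dose = (consent − test) + (first dose − consent) ≤ 14 + g.

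| Assumed g (days) | Oldest compliant test at first dose (days) | With a 7-day limit before first dose (days) |
|---|---|---|
| 0 | 14 + 0 = 14 | 7 |
| 7 | 14 + 7 = 21 | 7 |
| 14 | 14 + 14 = 28 | 7 |

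Only the first row needs no assumed gap.

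**Step 2. Does the general window close the gap?**
Suppose C.6.2 also applies to the test. Its registration alternative allows an age of up to 14 + r, which is still 14 days with same-day dosing. Its drug-start alternative would give 7 days, but the two are joined by *or*, so nothing obliges a site to meet the shorter one.

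**Step 3. What do the other protections cover?**
Contraception is required during the study. Assume that this starts at consent. The g days from consent to dosing are then covered, and the days between test and consent are not. Under the current rule that uncovered stretch is at most 14 days, whatever g is. With a 7-day limit before first dose it is at most max(0, 7 − g): 7 days when g = 0, and 0 days when g is 7 or more. The stop for suspected pregnancy discontinues study drug, so it acts only once dosing has begun.

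**The case against.** The strongest reply is that this is a preference for a tighter window. The rule is clear and stated twice in the same words. It sets only the earliest date, so a test at or after consent is allowed, and Table 3 places it at Baseline. Sites may dose promptly. Contraception, including by male partners, probably covers the time from consent to dosing. A negative test misses very early pregnancy whatever its date. Consent pages were not in the reviewed text, so a timing rule elsewhere cannot be excluded.

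Much of this stands, and it keeps the point minor. It does not remove it: a later test is permitted but not required, and no rule in the reviewed text requires a recent negative result at first dose.

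Three stronger readings are tempting, and the documents do not support them:

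- **That the plan leaves it unclear which part of the baseline window governs the test.** The test has its own specific rule, which on ordinary reading prevails over a general window that does not name it.
- **That criterion 6 shows the plan treating hemoglobin more strictly.** It says: "If the patient has not had blood drawn for a hemoglobin level in the previous two weeks, one will be performed to determine eligibility". That is a two-week window tied to enrollment. It supports neither a 7-day limit nor a first-dose anchor. Criterion 12 already implies a new test when the available one is too old at consent.
- **That counting birth control from the last dose conflicts with counting the test from consent.** The 30 days set when contraception ends; it starts with the study. There is no inconsistency.

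**Conclusion.** The point holds as a minor patient-safety correction worth considering, with medium confidence. The plan states a timing rule but counts from the wrong event. A compliant negative test can be 14 + g days old at first dose: 14 days with no assumed gap, and more only if there is a gap, whose length the reviewed text does not give. A 7-day limit before first dose would hold the age at 7 days whatever g is.

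A reader might take the 21- and 28-day figures as what happens in this trial, or as a measure of fetal exposure. They are neither. They are the largest test ages the rule allows under assumed gaps, and the documents give no basis for estimating how many women, if any, would be affected. Nor is there any consequence for sample size, power, type I error or the planned analyses.

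**What to change.** In criterion 12 and in the Table 3 footnote, replace the consent anchor with:

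*Negative pregnancy test within 7 days before the first dose of study drug, obtained before randomization (before registration in Phase I); repeat before dosing if the first dose falls more than 7 days after the test.*

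Seven days is the drug-start alternative already in C.6.2, so no outside standard is needed. Testing before randomization keeps the first result an entry criterion.

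**Cost.** Two wording changes and an occasional repeat test. If dosing is delayed after randomization, a repeat test could, rarely, turn positive and exclude a woman who has been randomized but not dosed. She would fall outside the plan's evaluable set, which is "any patient enrolled on the study that has taken at least one dose of treatment". Any such case should be reported by arm.

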We will summarize patient characteristics of all patients enrolled in the pilot study. Means and standard deviation or medians and IQRs will be calculated. We will also perform exploratory analyses on the changes in FACIT-F subscale (primary outcome measure) from baseline to Day 29 and baseline to Day 57. Similar analysis will be conducted for the secondary outcomes (FACT-G, ESAS symptoms, HADS, SDMT, six- minute walk test, Borg Scale, GSE and Hand Grip Strength and Endurance Test). Based on whether the data is normally distributed (Shapiro-Wilk test) we will use paired t-tests or Wilcoxon Ranked Sum tests. We will also summarize fatigue scores, other secondary outcomes at each point in time and the frequency and type of side effects as determined by NCI CTCAE V4 criteria.

Safety Monitoring

Safety Monitoring

Because this Panax ginseng has not been previously evaluated in cancer related fatigue, we will implement this study in two phases and we will utilize early stopping rules for dose-limiting toxicities (DLTs) for 30 patients in the treatment arm (Arm 2, Panax ginseng 800mg/day) before the main phase of the study begins. A DLT is defined as any Grade 3 or 4 toxicity that is attributable to the treatment regimen.

In the first phase, we will enroll up to 30 evaluable patients in the Arm 2 (treatment arm); patients will not be enrolled in the placebo arm. Recruitment for the main study will be delayed until these original 30 patients are evaluated for DLTs. We will base early stopping rules on a method proposed by Thall et al., (160) and using the Multc99 software from the Department of Biostatistics.

To ensure that the true DLT rate is sufficiently low, we will terminate the study early if the probability that the estimated toxicity rate is greater than 10% (given the results) is greater than 0.95. We assume a prior of Beta (0.1,0.9) in these calculations. The study will be stopped early if (# patients with DLT) / (# patients evaluated) >= 3/6, 4/10, 5/16, 6/22, or 7/29.

The table below shows operating characteristics given differing true toxicity rates based on 10000 simulations for each row:

	Probability	Achieved Sample Size		
True DLT rate	Early Stopping	25 th , 50 th , 75 th percentiles		
1%	<0.0001	30	30	30

Operating Characteristics for first phase early stopping rule (based on DLT)

3%	0.002	30	30	30
5%	0.013	30	30	30
8%	0.053	30	30	30
10%	0.116	30	30	30
15%	0.324	20	30	30
20%	0.597	9	21	30
25%	0.791	8	14	27
30%	0.917	6	9	17
40%	0.993	6	7	9

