During the second phase of the study, the DSMB will meet to assess toxicity in an unblinded fashion at defined intervals (annual review) and will terminate the study if the incidence of DLT on either arm is judged by the DSMB to be excessive.

Power Considerations: There are no randomized controlled trials on P.ginseng for the management of CRF. The only intervention with Level I evidence for effectiveness in CRF is exercise. Among the most important clinical trials conducted on the intervention are those of Segal etal [154-156]. They have determined the clinically important difference in fatigue as a result of intervention as compared to placebo. Since these two studies used FACIT-F (our primary outcome) we have used these studies for power/sample size calculation. We postulate that if P.ginseng is an effective intervention we will observe a difference in response at Day 29(primary end point) similar and higher to those observed in the Exercise studies. We plan to include 50 evaluable patients per group. If we assume that our dropout rate will be no higher than 20%, we will recruit 64 patients into each group, for a total of 128 patients. As we could find no other published studies about the use of Panax ginseng in cancer patients, we base our sample size estimate on previous research in resistance exercise training [154]. This study found that the difference between groups in changes in the FACIT F subscale at 24 weeks was 4.78, significant at p=0.002, and was powered to detect a difference of 3.5 points based on a similar study in exercise resistance [155] that found standard deviations in difference scores over 12 weeks of 5.8. Studies such as Cella et al, 2002[156], state that differences of 3-5 points or more on the FACIT-F subscale are clinically important differences. If we assume a standard deviation of 5.8 in difference scores, with 50 evaluable patients per group we will be able to detect differences as small as 3.3 or larger with a twosided significance level of 0.05 and 80% power. With standard deviations in difference scores as large as 8.8, we will still be able to detect differences of 5 points or greater.

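### The Phase I stopping rule has no DLT observation window, so a dosed patient who leaves early without a recorded DLT counts as DLT-free and stopping is somewhat less likely than stated

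*Combined protocol and SAP*

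**What the plan says.** Section C.6 (Clinical Trial Design and Treatment Plan) states: "Evaluable patients will be defined as any patient enrolled on the study that has taken at least one dose of treatment", with the stated consequence of "making them available for toxicity and response". The opening text of C.9 (Statistical Analysis) repeats that a single dose is enough to be analysed for toxicity. Phase I is sized at 30 such patients, all on ginseng.

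C.9, Safety Monitoring, defines the event by grade and attribution alone: "A DLT is defined as any Grade 3 or 4 toxicity that is attributable to the treatment regimen". The plan will "terminate the study early if the probability that the estimated toxicity rate is greater than 10% (given the results) is greater than 0.95". It adds: "We assume a prior of Beta (0.1,0.9) in these calculations". The resulting boundaries, as patients with a DLT over patients evaluated, are 3/6, 4/10, 5/16, 6/22 and 7/29. A table of stopping probabilities from 10,000 simulations per row follows. The randomised phase waits on the result: "Recruitment for the main study will be delayed until these original 30 patients are evaluated for DLTs".

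The plan gives no DLT window, no minimum exposure and no rule for patients who leave before their status is known. For clinical benefit, by contrast, C.9 does set a minimum: patients who have not reached Day 15 are inevaluable.

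The only dropout figure is in Power Considerations ("If we assume that our dropout rate will be no higher than 20"%) and concerns the 128 randomised patients.

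**The concern.** The stopping rule knows two states, DLT or no DLT. If one dose makes a patient evaluable, someone who leaves on Day 4 without an event carries the same weight in the denominator as someone observed to Day 29. Each such patient dilutes the observed rate. The operating-characteristics table treats every counted patient as having had the full chance to show a DLT, and the evaluability definition does not secure that.

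The error runs in one direction, towards less stopping. The rule is also the check that stands between 30 open-label patients and the 128-patient randomised phase. A one-dose set is normal for describing toxicity; the difficulty is its use as the denominator of a stopping boundary.

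**Working it through.** **Inputs.** From C.9: prior Beta(0.1, 0.9), threshold DLT rate 10%, posterior cut-off 0.95, maximum 30 patients, and the listed boundaries. The share of DLTs that go unseen is not in the documents; it is assumed at 5%, 10% and 20%.

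**Step 1: the boundary.** After r DLTs in n patients the posterior is Beta(0.1 + r, 0.9 + n − r). Stop if P(rate > 0.10) > 0.95.

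- 3/9 gives 0.955 (stop); 3/10 gives 0.940 (continue)
- 4/15 gives 0.952 (stop); 4/16 gives 0.940 (continue)
- 5/21 gives 0.954 (stop); 5/22 gives 0.945 (continue)
- 6/28 gives 0.951 (stop); 6/29 gives 0.942 (continue)

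So 3 DLTs are needed at n = 6–9, 4 at 10–15, 5 at 16–21, 6 at 22–28 and 7 at 29–30. Each listed pair is the first n at which that count applies.

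**Step 2: reproduce the plan's table.** This is an exact binomial recursion, with a look after every patient from n = 6 to 30 and every status known.

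| True DLT rate | Stated | Recomputed |
|---|---|---|
| 10% | 0.116 | 0.112 |
| 15% | 0.324 | 0.332 |
| 20% | 0.597 | 0.592 |
| 25% | 0.791 | 0.798 |
| 30% | 0.917 | 0.919 |
| 40% | 0.993 | 0.993 |

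The table is right under complete observation.

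**Step 3: early leavers counted as DLT-free.** If a share d of DLTs goes unseen while the patients stay in the denominator, the rule sees a rate of p × (1 − d). For example, p = 0.20 and d = 0.10 gives 0.18. Stopping probabilities:

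| True rate | d = 0 | d = 5% | d = 10% | d = 20% |
|---|---|---|---|---|
| 10% | 0.112 | 0.097 | 0.082 | 0.057 |
| 20% | 0.592 | 0.542 | 0.490 | 0.384 |
| 30% | 0.919 | 0.891 | 0.856 | 0.764 |

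**Step 4: how a leaving rate maps to d.** For 20% of patients leaving to hide 20% of DLTs, no leaver may contribute any DLT information. Two milder cases:

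- 20% leave at half exposure with constant hazard. The observed rate is 1 − [0.8(1 − p) + 0.2(1 − p)^0.5], which is 0.181 at p = 0.20 and 0.273 at p = 0.30. Stopping is 0.496 and 0.863.
- 20% leave at uniform times, with DLT times also uniform. Half of the leavers' DLTs are seen, so the observed rate is p(0.8 + 0.2 × 0.5) = 0.9p. Stopping is 0.490 and 0.856.

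Both land close to the 10% column.

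**Step 5: the repaired rule.** Thirty patients are dosed, 20% leave at uniform times and none is replaced. Patients are taken in enrolment order, and each counts only with a DLT or a completed window. Each dosed patient is a counted DLT with probability 0.9p, a counted non-DLT with probability 0.8(1 − p), and otherwise uncounted. At p = 0.10 these are 0.09, 0.72 and 0.19. Stopping is 0.134, 0.612 and 0.917 at true rates of 10%, 20% and 30%, close to the stated 0.116, 0.597 and 0.917.

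**The case against.** **The denominator is not settled by the text.** The boundary speaks of patients evaluated, not evaluable, and the main study waits until the 30 have been evaluated for DLTs. A team could read this as requiring a completed assessment. That reading is possible, but no passage says what a completed assessment is. The only definition offered makes one dose sufficient for toxicity, so followed as written the leaver counts.

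**Leaving treatment is not the same as being unobserved.** This stands and limits the size. C.6.2 schedules toxicity checks on Days 8, 15, 21 and 29 and follows patients for up to 30 days after the last dose. C.8 captures serious events for 30 days after the last dose unless consent is withdrawn. A patient who leaves because of a DLT is counted. What remains is the DLT that needed further exposure, the patient lost or withdrawing consent, and laboratory toxicity. Outside laboratories are allowed, but C.6.2 also limits collection of the Day 15 and Day 29 safety labs to patients who return to the centre.

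**The 20% belongs to the randomised phase.** This also stands. A reader might infer that the plan expects 20% early leaving in Phase I, and hence a fall to 0.38 at a true 20% rate. The documents support neither step: no Phase I figure exists, and a missed Day 29 questionnaire is not a missed Grade 3 or 4 toxicity.

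**The table could still hold** if the true DLT rate meant the rate per dosed patient whatever the exposure. The plan does not say so.

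**Conclusion.** The point holds as a cheap improvement. The plan counts anyone with one dose as evaluable for toxicity and gives no DLT window, so its stopping rule can absorb early leavers as DLT-free, while its stated operating characteristics assume complete observation.

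The size depends on an unstated quantity. With 5% or 10% of DLTs unseen, stopping at a true 20% rate falls by about 5 or 10 percentage points, and at 30% by about 3 or 6. The 20% column of step 3 is the extreme case. These figures assume that leavers without a recorded DLT stay in the denominator and that the boundary is checked after every patient from the sixth.

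A reader might also infer that the operating-characteristics table is miscalculated. It is not; it reproduces to within one percentage point.

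**What to change.** For the stopping rule only, add to Safety Monitoring in C.9:

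- The DLT window runs from first dose to Day 29.
- A patient is DLT-evaluable if a DLT occurs in the window or the window is completed without one.
- Boundaries are applied in enrolment order, once each patient's status is complete.
- Leavers without a DLT are not counted and need not be replaced.
- The operating-characteristics table is confirmed under this definition.

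The one-dose set stays for the descriptive toxicity tables.

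The enrolment-order condition matters. If a DLT entered at once but a non-DLT only at Day 29, the rule would over-stop. A simulation with no leavers, DLT times uniform over 29 days and accrual of 2, 5 or 10 patients a month (all assumed) gave 0.13, 0.16 and 0.21 at a true 10% rate, against 0.116 stated.

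The cost is a short paragraph and one re-run of the table. Fewer than 30 patients may be counted: about 24 of 30 in the step 5 example at a true 10% rate (30 × 0.81 = 24.3), and closer to 30 with less leaving. Stopping is slightly more frequent at an acceptable rate, about 0.13 against 0.116 at a true 10% with 20% leaving. If the team prefers a full 30 DLT-evaluable patients, about 32, 34 or 38 would have to be dosed at 5%, 10% or 20% uninformative leaving (30/0.95, 30/0.90, 30/0.80, rounded up).
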